Study Title:

Intercostal Liposomal Bupivacaine for the Management of Blunt Chest Wall Trauma

Research Team:

Principal Investigator:

[name]

Co-Principal Investigator:

[name]

1. Length of time for research

- a. Subject enrollment, data collection, and regulatory reporting: 18 months
- b. Statistical analysis of data: 2 months
- c. Manuscript and poster preparation, writing, and publication: 4 months

2. Research Location(s): University of Cincinnati Medical Center (UCMC) and UC Medical Science Building

3. Abstract/Brief Overview:

Polytrauma patients with rib fractures are at risk for poor pain control resulting in adverse pulmonary outcomes, including the development of pneumonia or respiratory failure. Liposomal bupivacaine provides a novel medication and administration route that may prevent the need for rescue intubation and development of pneumonia, avoid epidural use, and improve overall patient satisfaction and pain control. This study plans to enroll adult, polytrauma patients with blunt chest wall trauma resulting in rib and/or sternal fractures to receive either liposomal bupivacaine or normal saline intercostal nerve injections in addition to current standard of care (including intravenous, oral, or epidural narcotics). Patients will be excluded if they have a known allergy to bupivacaine, respiratory failure requiring intubation within 24 hours of enrollment, have a known atrioventricular nodal blockade process, hemodynamic instability, active myocardial infarction, greater than 20 rib fractures, or if they are pregnant or actively incarcerated. The purpose of this study is to evaluate the efficacy of liposomal bupivacaine to provide analgesia via posterior intercostal nerve block following significant blunt chest trauma, minimizing adverse outcomes and length of stay and overall narcotic use. The primary outcome of this study is to compare opioid requirements between groups. Secondary outcomes include comparison of clinical outcomes and treatment failures (e.g., development of pneumonia; median patient analgesic score by verbal numerical rating scale [NRS]; median time to first breakthrough opioid dose; incentive spirometer [IS] ability; intensive care unit [ICU] length of stay [LOS]; hospital LOS; use of additional analgesia adjuncts) and to perform a cost effective analysis.

4. Purpose of Study:

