The primary purpose of this pilot study is to compare opioid requirements between groups receiving intercostal liposomal bupivacaine to standard of care for acute traumatic pain related to blunt chest wall trauma with resultant rib and/or sternal fractures. Pain scores will be evaluated using the NRS (Appendix). Uncontrolled analgesia following rib fractures can result in intubation, pneumonia, prolonged length of stay, and death. Achieving adequate pain control in native airway patients prevents clinical challenges. Multimodal analgesia regimens are necessary to optimize patient outcomes and prevent untoward

effects of opioid analgesia. Liposomal bupivacaine offers a novel therapy that may revolutionize pain management in patients with rib fractures. Pain control with one injection may provide analgesia for up to 96 hours through a unique mechanism of action and site of application. Overall, the combination of a nonopioid analgesic, liposomal bupivacaine, with standard of care may lead to improved analgesia with fewer adverse effects. Specific aims include to 1) compare opioid requirements (in morphine equivalents) between patients with blunt chest wall trauma and rib and/or sternal fractures receiving liposomal bupivacaine versus standard of care; 2) compare clinical outcomes and treatment failures including development of pneumonia, median patient analgesia score using verbal NRS, median time to first breakthrough opioid dose, IS ability, ICU LOS, hospital LOS, and use of additional analgesic adjuncts; 4) and to perform a cost-effectiveness analysis

5. Background:

Background and Significance

Blunt chest wall trauma remains the second most common injury observed in non-intentional injury-related death in the U.S.A. and accounts for 10% of trauma-related emergency department visits worldwide.¹⁻³ Current literature has identified high morbidity and mortality rates for patients suffering from blunt chest wall trauma, with mortality ranging from 4 to 20%.^{2,4} The prevalence of rib fractures among blunt chest wall trauma patients requiring hospital admission is 4 to 10%.⁵ One of the most prominent contributing factors to blunt chest wall trauma morbidity is pain.⁶⁻⁸ The management of resultant pain serves as a core intervention in managing these patients.⁸

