emergency medicine and surgery practitioners are familiar with intercostal blocks for placement of tube thoracostomy. Intercostal blocks do not require additional training, as would be done in the setting of a pain medicine fellowship, and do not incur the risks of hypotension associated with epidural catheters. Additionally, intercostal and paravertebral blocks carry similar risks of pneumothorax or intercostal neurovascular bundle injury.

Study design:

This is an investigator-initiated, single-center, prospective, double-blinded, placebo-controlled trial funded by the United States Air Force. Multi-system, adult trauma patients greater than or equal to 18 years of age admitted to the University of Cincinnati Medical Center (UCMC), an urban American College of Surgeons-verified Level 1 trauma center with more than 3500 annual trauma admissions annually will be identified by the research team. Patients will be screened and those who meet all inclusion/exclusion criteria will be approached for informed consent by study personnel in their rooms. Informed consent will be obtained prior to enrollment and any study procedures are done. Patients will then receive either receive 1 mL of liposomal bupivacaine just below each affected rib or 0.9% sodium chloride peri-intercostal subcutaneous injection (as placebo control) via a 25-G needle. Goal enrollment is 200 patients with 100 patients in each group. Patients included in the study will be followed during inpatient hospitalization through discharge.

6. Research data collection/study procedures:

Intervention

Patients will be identified on admission and will be screened by inclusion/exclusion criteria. After informed consent is obtained they will be randomized into one of two possible groups:

- a. Liposomal bupivacaine intercostal (group 1; interventional)
- b. 0.9% sodium chloride peri-intercostal subcutaneous (group 2; placebo-control)

Patients will be placed on continuous monitoring of heart rate, EKG, and pulse oximetry. Blood pressure and respiratory rate will be measured every 5 to 10 minutes during the procedure and every at least 15 minutes for the first hour after the procedure. All patients undergoing injection will remain on heart rate, EKG, and pulse oximetry monitoring by telemetry for 96 hours following injection.

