A chest xray will be obtained as clinically indicated following the procedure if there is concern for the development of pneumothorax.

Self-reported pain will be measured using the verbal NRS, a 0-10 ordinal scale (e.g., 0 = "no pain"; 10 = "worst pain imaginable").²⁷ Breakthrough opioid dosing

will be guided by a formal inpatient analgesia protocol. Pain assessments will occur every 6 hours or per standard of care for the appropriate setting (e.g., intensive care unit, trauma ward) for the first 96 hours. All opioid dosing will be converted to oral morphine equivalents for comparison purposes. Time to first breakthrough opioid dose will be recorded. Incentive spirometry will be used and assessed and recorded by respiratory therapist, with adjunct inspiratory assistance (e.g., EzPAP) applied per our institutional volume expansion protocol.

Follow-up will occur daily by study coordinators and trauma service physicians for the first 96 hours after block procedure, then daily by the trauma service physicians for 14 days or until discharge from the hospital if it occurs earlier.

Standard of care analgesia regimen on the trauma service will be provided to all patients enrolled in the study, regardless of liposomal bupivacaine or placebo injection. This regimen will be per the Trauma acute multimodality pain management protocol (Appendix).

Typical escalation of analgesics provided for these patients, as deemed medically appropriate based on age and comorbid medical conditions, includes (in order of addition to regimen):

- Acetaminophen, oral or enteral
- NSAIDs, ibuprofen or ketorolac
- Lidocaine 5% transdermal patch
- Oral or enteral tramadol
- Oral or enteral hydrocodone or oxycodone
- IV morphine or hydromorphone, intermittent dosing
- Patient controlled analgesia morphine or hydromorphone
- Long-acting narcotics, including methadone, oxycodone ER, or morphine ER
- Neuromodulating adjuncts, including gabapentin or pregabalin
- Epidural analgesia catheter placement

During this time all adverse events will be recorded. Subjects who experience serious adverse events will be followed until the event resolves. If necessary these patients will be followed up by weekly phone calls as well as at the standard of care clinic visit two weeks post-discharge.

Randomization

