Following informed consent, patients will undergo 2x1 block randomization to ensure equal allocation to each intervention group. Randomization will be performed by study personnel and will be blinded as there will be placebo injections for patients randomized into group two and the same number of injections would be used regardless of intervention arm.

Data Collection:

Verbal NRS, pain assessment data, opioid use, and time to first opioid breakthrough dose will be collected as previously described. Portable spirometry will be used daily to objectively and serially assess lung function. Additional data collection points include patient sex, age, weight, body mass index, body surface area, injury severity score, chest abbreviated injury score, and ICU and hospital length of stay. Safety will be evaluated by the occurrence of *a priori* serious adverse events. Costs will be evaluated utilizing hospital and pharmacy databases.

Schedule of subject identification and data collection

Subjects will be identified based on inclusion criteria at the time of admission to the trauma service following evaluation in the emergency department. Subjects meeting inclusion criteria will be enrolled within 6 hours of admission. Vitals monitoring will occur during the intercostal nerve block procedure and continue by telemetry for the next 96 hours or until hospital discharge, whichever occurs first.

7. Specimen collection:

No serum assays are necessary for this study and will not be collected.

8. Potential Benefits:

Blunt chest wall trauma remains a common injury seen in non-intentional injury-related deaths. It accounts for nearly 10% of trauma-related emergency department visits worldwide and is associated with high morbidity and mortality. This morbidity and mortality are influenced by the pain experienced by these events which can involve rib or sternal fractures as instigating stimuli.

Uncontrolled analgesia following rib fractures can result in intubation, pneumonia, prolonged length of stay, and death. Achieving adequate pain control in native airway patients prevents clinical challenges. Multimodal analgesia regimens are necessary to optimize patient outcomes and prevent untoward effects of opioid analgesia (e.g., hypotension; bradycardia; central nervous system depression; respiratory depression).

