 - Repeat bolus once or twice for persistent cardiovascular collapse
 - Double the infusion rate to 0.5 mL/kg/min if blood pressure remains low
 - Continue infusion** for at least 10 minutes after attaining circulatory stability
 - Recommended upper limit: Approximately 10 mL/kg lipid emulsion over the first 30 minutes
- Post LAST events at www.lipidrescue.org and report use of lipid to www.lipidregistry.org**

TRAUMA ACUTE MULTIMODAL PAIN MANAGEMENT PROTOCOL

(Originated 07/14; revised 11/14; reviewed 06/15)

OBJECTIVE

Provide a multidisciplinary trauma service protocol for acute pain management in non-intubated, alert and oriented patients (GCS 15) with transition through inpatient and outpatient settings.

Medication and Injury-Specific Guidelines

Rib fractures (≥ 2 ribs):

1. Lidocaine 5% transdermal patch
 - a. Apply 1-2 patches to affected area
 - b. Apply for 12 hours and remove for 12 hours
 - c. Do not apply to open cuts or abrasions
 - d. Use caution if applied for > 7 days
2. Epidural
 - a. Consider AIPS consult
3. IV Acetaminophen
 - a. Restricted to patients who are NPO with no feeding access
 - b. Patients must be ≥ 65 years old with ≥ 2 rib fractures
 - c. Patients can only receive IV acetaminophen for 24 hours or until PO/FT status confirmed, whichever comes first
 - d. All other IV acetaminophen use is subject to a non-formulary request per current UC Health policies and procedures

Non-steroidal anti-inflammatory drug (NSAIDs)

4. Allowable in orthopedic fractures EXCEPT:
 - a. Tibia shaft fracture
 - b. Humerus shaft fracture
 - c. Spine fractures/surgeries
 - d. Any non-union or fusion surgeries

Nerve Injury / Burn Injury / Neuropathic Pain

5. Gabapentin
 - a. Start at 300 mg q8h
 - i. Elderly (age ≥ 65 years), low-weight (≤ 50 kg), or renal dysfunction (CrCl ≤ 30 mL/min) will require dose reduction to daily administration
 - b. Up titrate q72h as needed based on patient response
 - c. Caution in patients with altered mental status

History of Narcotic / Heroin Abuse / High Pain Scores or Tolerance

6. Initiate patient home medications as able
 - a. If on formulary, initiate home dose

- b. If non-formulary, consult pharmacy for appropriate conversion
- 7. Early Methadone initiation should be initiated for early pain control in patients with high pain scores or opioid tolerance
 - a. Initiate the lowest effective dose and up/down titrate as able
 - b. Up titrate q48-72h as needed based on patient response

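### Continued home opioid counts toward the primary total, yet pre-injury opioid use is not recorded, stratified on or adjusted for: a loss of precision, not a bias

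*Combined protocol and SAP*

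**What the plan says.** **What is counted.** Section 6 (Intervention): "All opioid dosing will be converted to oral morphine equivalents for comparison purposes". No opioid is set aside by source or indication.

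**Who is enrolled.** Section 5 (Study design): "Multi-system, adult trauma patients greater than or equal to 18 years of age". None of exclusions a to k in Section 13 concerns chronic opioid use, opioid use disorder or methadone maintenance.

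**What they receive.** Section 6 gives all enrolled patients the appendix pain protocol. Under its heading on narcotic history and tolerance, that protocol says "Initiate patient home medications as able" and "Early Methadone initiation should be initiated for early pain control in patients with high pain scores or opioid tolerance".

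**What is recorded.** Section 6 (Data Collection): "Additional data collection points include patient sex, age, weight, body mass index, body surface area, injury severity score", followed by the chest injury score and lengths of stay. Pre-injury opioid use is not listed. The Randomization paragraph names no stratification factor.

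**How it is analysed.** Section 11 plans a t-test or a rank-sum test, chosen by distribution, with no covariates.

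**The aim.** Section 4 sets the comparison within "standard of care for acute traumatic pain related to blunt chest wall trauma with resultant rib and/or sternal fractures". Aim 1 in the same section is to "compare opioid requirements (in morphine equivalents) between patients with blunt chest wall trauma and rib and/or sternal fractures receiving liposomal bupivacaine", without dividing opioid by pain site. Section 3 also gives as a purpose "minimizing adverse outcomes and length of stay and overall narcotic use".

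**The concern.** A patient on long-term opioid who has it continued in hospital carries that amount into the 96-hour total, whatever the block does. Section 11 expects a 50 mg difference on a control mean of 250 mg. Someone on 120 mg/day at home would bring 4 × 120 = 480 mg, nearly ten times that difference. A modest share of such patients widens the spread of the primary endpoint.

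Two things are at stake. The first is precision: a real effect may be missed. The second is interpretation: if one arm happens to receive more such patients, the listed data items would not reveal it. Under Section 12 the subject log is destroyed at study end, so the information could not be recovered from charts afterwards.

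**Working it through.** **Inputs from the documents.** Section 11: control 250 mg, treated 200 mg, difference 50 mg, SD 50 mg, alpha 0.05, 80% power, 200 patients. Section 5: 100 per arm. Sidedness is not stated; two-sided is assumed.

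**Assumed inputs.** Share f of patients on home opioid; home dose M in mg/day of oral morphine equivalents, fully continued for four days; SD σ in the total apart from home opioid. The documents give neither f nor M.

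**Step 1: the plan's own figure.** n per arm = 2 × (1.960 + 0.842)² × (50/50)² = 15.7, so 16 (17 with the t distribution), or 32 to 34 in total. The stated 200 is not reproduced. That is a separate matter, but it gives the plan a reserve. At 100 per arm the standard error is 50 × √(2/100) = 7.1 mg and power exceeds 99.99%. Power falls to 80% only when the total SD reaches 50 / (2.802 × √0.02) = 126 mg.

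**Step 2: add home opioid, keeping σ = 50 mg.** SD = √(σ² + f(1−f)(4M)²); SE = SD × √(2/100); t-test power = Φ(50/SE − 1.96). Middle case: √(2,500 + 0.09 × 480²) = √23,236 = 152 mg. Rank-sum power is from simulation.

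| f | M (mg/day) | SD (mg) | SE (mg) | t-test power | rank-sum power |
|---|---|---|---|---|---|
| 5% | 60 | 72 | 10 | 99.8% | about 100% |
| 10% | 120 | 152 | 22 | 64% | >99.9% |
| 15% | 200 | 290 | 41 | 23% | 99.8% |

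**Step 3: a wider spread in other patients.** Section 11 gives no source for the SD of 50 mg. Take σ = 100 mg as an assumption, with home doses averaging 120 mg/day and varying between patients (simulation).

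| f | t-test | rank-sum | adjusted for recorded home dose |
|---|---|---|---|
| 10% | about 48% | about 82% | about 94% |
| 20% | about 32% | about 66% | about 94% |

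The t-test column can be checked by formula. If the SD of home doses is half their mean, the added variance is 480² × (1.25f − f²). For f = 10% this is 26,496, so SD = √36,496 = 191 mg, SE = 27.0 mg and power 46%. For f = 20% it is 48,384, so SD = 242 mg, SE = 34.2 mg and power 31%. The figures move by a few points with the assumed spread of doses. The adjusted column is the power with the home-opioid variance removed: SE = 100 × √0.02 = 14.1 mg, and Φ(3.54 − 1.96) = 94%.

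**Step 4: chance imbalance.** Shifting a 100-patient mean by 50 mg takes 100 × 50 = 5,000 mg of excess. That is about 21 extra home-opioid patients at 240 mg, 11 at 480 mg and 7 at 800 mg. In the three cases of Step 2 the simulated chance of such an imbalance, in either direction, is about 0%, 1.3% and 20%. A shift of half the planned effect is easier. In the middle case the home-opioid part of the arm difference has SE = 144 × √0.02 = 20.4 mg, so a shift of 25 mg or more occurs with probability 2 × (1 − Φ(1.23)), about 22%.

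**Step 5: false positives.** With no true effect, simulated rejection rates in the Step 2 cases were 4.9–5.9% for both tests.

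**The case against.** The strongest reply is that Section 11 already assigns the rank-sum test to non-normal data. The Step 2 scenarios are plainly non-normal: a normality test rejected in at least 97% of simulated trials in every case. The rank-sum test then keeps over 99% power. This stands for σ = 50 mg, and the 64% and 23% figures should not be quoted without it. It does not settle the matter. Section 11 leaves the choice of test open until the data are seen, and the protection weakens once σ is larger (Step 3).

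Four stronger readings are tempting and are not supported.

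- *The endpoint does not measure the objective.* The chest-wall phrase in Section 4 gives the indication. Aim 1, the Section 11 endpoint and the purpose in Section 3 all fit an all-opioid total. Replacing it with a net total would be a choice of estimand, not the repair of an error.
- *Chance imbalance produces false differences.* Randomisation balances home opioid on average, and the type I error stays near 5%.
- *A few patients can cancel or mimic the planned effect.* Step 4 supports this only at the highest assumed dose and share.
- *Operating-room opioids are a documented contaminant.* The perioperative remark in Section 9 is about withholding enoxaparin doses and does not mention opioids.

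Opioid given for other injuries could also dilute the effect. However, the documents give no chest-wall share, and the planned 50 mg is already stated on the whole 96-hour requirement. That point is not pressed here.

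**Conclusion.** The point holds as one of avoidable imprecision. Patients on long-term opioid are eligible and foreseen, their continued doses enter the primary total, and nothing in the listed data, the randomisation or the analysis accounts for it. The consequence is lost precision, and a chance imbalance that could not be seen.

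The size is conditional. On the plan's SD of 50 mg the loss is serious only if the t-test is used, and then only towards the higher assumed shares and doses. With an assumed SD of 100 mg and 10–20% of patients averaging 120 mg/day, both planned tests fall well short of the 94% that adjustment would give. That 94% assumes home doses are recorded accurately and continued in full; errors in either would lower it. The change is worth making because it is cheap, not because the trial is shown to fail without it.

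**What to change.** **Section 6.** Before randomisation, record pre-injury opioid use from the admission medication history: yes or no, and daily oral morphine equivalents where known. Stratify the block randomisation by yes/no.

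**Section 11.** Keep the all-opioid 96-hour total as the primary endpoint. Pre-specify one primary analysis adjusted for the recorded pre-injury dose and the stratum, for example a linear or rank-based ANCOVA, in place of a choice of test made on the observed distribution. State how an unknown dose is handled. Adjust only for use before injury: opioid started after randomisation, including early methadone for high pain scores, may respond to the block and should stay in the outcome. As a sensitivity analysis, report the total net of home opioid actually continued. Subtracting doses given, rather than the recorded home dose, avoids negative totals where home drugs were not restarted.

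**Cost.** One or two baseline fields, one stratification factor, and a flag on continued home doses for the sensitivity analysis. Home doses will be imprecise for some patients, such as those with illicit use; for them the yes/no stratum carries most of the information. No treatment changes.
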